8.1 Overall Study Design

Explorative non-interventional prospective study. The choice of therapeutic intervention are determined at the discretion of the gastro-enterologist according to standard clinical practice. Several interventions are scheduled in addition to standard clinical practice.

8.2 Study Duration for Subjects

8.2.1 Screening

Screening will last about 15 minutes to check the subject's eligibility either as IBS patient or healthy subject. Informed consent will be obtained.

Eligible subjects will receive instruction on how to fill in the 4dFD. The 4dFD should be filled in during the week following the first visit.

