6.7 Study Activities

	Screening	Visit 1	Subsequent visits (for patients)
Inclusion/exclusion	X		
Informed consent	X		
Rome IV	X		
Clinical parameters		X	X
Intervention type		X	X
Psychological ques-		X	
tionnaires			
IPAQ		X	X
Four Day Food Diary		X	X
BIA		X	X
IBS-SSS		X	X

7 **Study Objectives and endpoints**

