7.3 Endpoints

The primary endpoint of this study is to explore whether PhA differs between IBS patients and healthy volunteers at visit 1.

The secondary endpoints are multiple and are divided in two parts.

The first part explores correlations at initial presentation among IBS patients and healthy subjects:

- Correlation of PhA with IPAQ
- Multiple regression of IBS status with multiple independent variables (PhA, IPAQ, dietary and FODMAP intake, psychological variables, gender)

In the second part, we want to explore changes of PhA according to changes in IBS-SSS in IBS patients only.

8 Investigational Plan

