8.2.3 Subsequent visits

Only IBS patients will attend subsequent visits.

The 4dFD should be filled in during the week preceeding the visit.

As much as possible, visits will take place on the same day as the visit to the outpatient clinic. Patients will be instructed to refrain from eating, drinking and smoking for 6h before attending the visit. During these visits the prescribed intervention will be recorded.

During the subsequent visits, IBS patients will fill in several questionnaires:

- IBS-SSS
- IPAO

BIA will be performed.

Each subsequent visit will last 30 minutes.

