10.1.2 First visit

Study participants should be fasting for 6h when attending the first visit.

The 4dFD should be filled in during the week preceding the visit. Clinical parameters of both IBS patients and healthy subjects will be recorded during the first visit.

During first visit, participants will fill in several questionnaires:

- IBS-SSS
- Psychological parameters:
 - o GAD-7
 - o PHQ-9
 - o PHQ-15
 - o VSI
- IPAQ

BIA will be performed.

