10.2.6 Dietary and FODMAP intake

Dietary and FODMAP intake will be evaluated by the 4dFD (appendix 8) at each visit.

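### Sections 8.2.1 and 10.1.2 set opposite weeks for the baseline food diary, so baseline diet may be recorded after a treatment choice in IBS patients only

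*Combined protocol and SAP*

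**What the plan says.** Screening and visit 1 are separate contacts in the schedule (section 6.7) and in sections 8.2.1 and 8.2.2. Diary instructions are given at screening. The timing rules for the diary are:

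- Section 8.2.1, baseline: "The 4dFD should be filled in during the week following the first visit".
- Section 10.1.2, baseline: "The 4dFD should be filled in during the week preceding the visit".
- Section 8.2.3, later visits, IBS patients only: "The 4dFD should be filled in during the week preceeding the visit". Section 10.1.3 agrees.
- Section 10.2.6: "Dietary and FODMAP intake will be evaluated by the 4dFD (appendix 8) at each visit". It gives no before-or-after window, and neither does the schedule.

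On treatment, the schedule marks "Intervention type" at visit 1 and at subsequent visits. Section 8.1 leaves the choice of therapy to the gastro-enterologist under standard practice, and section 6.3 names dietary intervention as one class of treatment.

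On analysis, section 7.3 introduces the first set of secondary endpoints with "The first part explores correlations at initial presentation among IBS patients and healthy subjects". One of these is a regression of IBS status in which dietary and FODMAP intake sits among the independent variables, with PhA, IPAQ, psychological variables and gender.

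**The concern.** Both baseline rules are current text and cannot both be followed. Staff working from section 8.2.1 would collect a different week from staff working from section 10.1.2, and the data would not show which rule had been used unless diary dates were kept.

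The two weeks are not interchangeable. A diary kept before visit 1 describes diet at presentation. A diary kept after it may, in IBS patients, describe diet after an intervention chosen at or around that visit. Healthy volunteers have no planned treatment, so any shift would fall in one comparison group only. The regression of IBS status could then show a diet difference produced by advice and not by the condition. A baseline diary kept in the wrong week cannot be collected again later.

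**Working it through.** **Which rule fits the rest of the plan.** The plan states no figure on this point, so the first step is to compare the sections.

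| Source | What it implies for the baseline diary |
|---|---|
| 8.2.1 | Week after visit 1 |
| 10.1.2 | Week before visit 1 |
| 8.2.3, 10.1.3 | Week before each later visit |
| 10.2.6 | Intake evaluated at each visit; a diary not yet kept cannot be evaluated at visit 1 |
| 8.2.1, 10.1.1 | Instructions given at screening, so a pre-visit diary is feasible |
| Appendices 5 and 7 | IPAQ looks back 7 days and IBS-SSS 10 days, so a post-visit diary would cover a different week from IPAQ in the same regression |
| 8.2.3 | Healthy volunteers have no later visit, so a post-visit diary has no scheduled return point for them |

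Everything except the one sentence in 8.2.1 points to the preceding week.

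**Illustrative size of the bias.** The documents give no inputs, so all of these are assumptions:

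- share of IBS patients given dietary advice by the time of the diary: 25% to 75% (midpoint 50%);
- proportional cut in FODMAP intake among those advised: 30% to 50% (midpoint 40%);
- between-person coefficient of variation (CV) of intake: 40% to 50% (midpoint 45%);
- no true diet difference between groups, and all IBS patients following 8.2.1.

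The fall in the IBS mean is share × cut: 0.25 × 0.30 = 7.5%; 0.50 × 0.40 = 20%; 0.75 × 0.50 = 37.5%.

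The false standardised difference is d = (share × cut) / CV. For normally distributed intake with equal SDs, a logistic regression of IBS status on diet alone gives an odds ratio of exp(d) per SD lower intake.

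| Case | d | Odds ratio |
|---|---|---|
| Low | 0.075 / 0.50 = 0.15 | 1.16 |
| Midpoint | 0.20 / 0.45 = 0.44 | 1.56 |
| High | 0.375 / 0.40 = 0.94 | 2.55 |
| Midpoint, half the IBS patients following 8.2.1 | 0.5 × 0.44 = 0.22 | 1.25 |
| No dietary advice before the diary | 0 | 1.00 |

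For scale, with 20 per group the standard error of d is about √(2/20) = 0.32. The midpoint bias is therefore about 0.44 / 0.32 = 1.4 standard errors, and the half-adherence case about 0.22 / 0.32 = 0.7.

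**Days needed for a pre-visit diary.** Appendix 8 asks for 3 weekdays and 1 weekend day. Any run of 6 consecutive days omits one day of the week. If that is a weekday, 4 weekdays and 2 weekend days remain; if it is a weekend day, 5 weekdays and 1 weekend day remain. Six days therefore always suffice. Five days fail only when they run Monday to Friday. Six full days between screening and visit 1 means visit 1 falls at least 7 days after screening.

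**The case against.** The strongest case against giving this much weight has four parts.

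*It is probably a slip.* Section 8.2.1 may have meant the week after screening, or may have written the wrong word. That is plausible, and it explains why the correction is so small. It does not remove the conflict: sections 8.2.2, 10.1.2 and 6.7 all use the first visit for something distinct from screening, and staff reading 8.2.1 literally would collect the wrong week. The study schematic is not reproduced in the text available, so it could not be checked for a window.

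*The treatment link is thin.* No section says therapy is chosen at visit 1. The entry in the schedule could record ongoing therapy, the visit 1 text in 8.2.2 and 10.1.2 does not list it, and the sentence "During these visits the prescribed intervention will be recorded" concerns later visits. This stands. The contradiction is certain; the bias is only possible.

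*The preceding week may be contaminated too.* Patients come from a gastroenterology clinic, and advice given at or before screening would also affect a pre-visit diary. A longer gap before visit 1 gives more time for that. This stands as well, and it is why the date of advice needs recording whichever week is used.

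*The size is assumed and the reach is narrow.* The range runs from zero to 0.94, the odds ratios ignore the other planned predictors, and a regression repeated on fewer than 40 people would be unstable. All of this is fair. The figures show what could happen and do not estimate what will. The need to reconcile the sections does not depend on them.

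**Conclusion.** The concern holds. Sections 8.2.1 and 10.1.2 give incompatible weeks for the baseline diary, and the rest of the plan supports the week before visit 1. This is an error in a stated rule, not a missing detail, and it should be corrected.

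The effect is confined to the dietary and FODMAP terms in one exploratory secondary regression and to the baseline for following diet over time. The comparison of PhA at visit 1, the PhA-IPAQ correlation and the analysis of PhA change against IBS-SSS change do not use the diary. Bias arises only if some IBS patients keep the diary after dietary advice. Confidence is high for the contradiction; the direction and size of any bias depend on treatment timing, which the documents do not give.

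**What to change.** 1. Change the sentence in section 8.2.1 so that both groups keep the baseline diary in the week before visit 1, matching sections 10.1.2, 8.2.3 and 10.1.3.
2. Schedule visit 1 at least 7 days after screening, so that the weekday and weekend pattern in Appendix 8 always fits.
3. Record the diary dates and the date of any dietary advice, including advice given at or before screening.
4. Flag diaries kept after visit 1 or after such advice. Keep them in the main regression and, as an optional sensitivity analysis, repeat it without them. Report that repeat with caution, given the small numbers.

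The cost is one sentence and two date fields. Diary instructions are already given at screening. Visit 1 may move back a few days for some participants, and the sensitivity analysis may rest on fewer than 40 people. The change concerns when data are collected and leaves treatment untouched.

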8.2.2 First visit

Participants will be instructed to refrain from eating, drinking and smoking for 6h before attending the first visit. Clinical parameters will be recorded.

During first visit, participants will fill in several questionnaires:

- IBS-SSS
- Psychological parameters:
 - o GAD-7
 - o PHO-9
 - o PHQ-15
 - o VSI
- IPAQ

BIA will be performed.

The first visit will last 30 minutes.

8.2.3 Subsequent visits

Only IBS patients will attend subsequent visits.

The 4dFD should be filled in during the week preceeding the visit.

As much as possible, visits will take place on the same day as the visit to the outpatient clinic. Patients will be instructed to refrain from eating, drinking and smoking for 6h before attending the visit. During these visits the prescribed intervention will be recorded.

During the subsequent visits, IBS patients will fill in several questionnaires:

- IBS-SSS
- IPAO

BIA will be performed.

Each subsequent visit will last 30 minutes.

8.2.4 Early Study Termination

No early study termination visit is required in this explorative non-interventional study.

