7.2 Secondary Objectives

The secondary objectives are double:

- Correlation of PhA with different parameters implicated in IBS pathophysiology in IBS patients and healthy subjects.
- Evolution of PhA according to response to therapy.

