8.2.5 End of Study

The study ends when the last study participant quits the study.

9 **Selection of Subjects**

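### Follow-up has no set time and leans on clinic attendance, so whether and when a patient has a PhA change value can depend on the treatment response under study

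*Combined protocol and SAP*

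**What the plan says.** The second secondary objective (7.2) is "Evolution of PhA according to response to therapy". Section 7.3 makes it an endpoint: "In the second part, we want to explore changes of PhA according to changes in IBS-SSS in IBS patients only". It needs at least two PhA and two IBS-SSS values per patient, and every value after the first comes from a subsequent visit.

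On those visits, 8.2.3 says "Only IBS patients will attend subsequent visits" and "As much as possible, visits will take place on the same day as the visit to the outpatient clinic". Sections 8.2.3 and 10.1.3 list what is measured but give no interval, window or minimum number of visits. The activities table in 6.7 has a single undated column for them. The schematic in 6.6 is not shown in the text available, so it may carry timing that cannot be seen here.

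On leaving, 8.2.4 says "No early study termination visit is required in this explorative non-interventional study", and 8.2.5 says "The study ends when the last study participant quits the study". Treatment is the gastro-enterologist's choice under standard practice (8.1). Section 11.4 gives the 20 + 20 recruitment target but no follow-up time point, analysis set, dropout allowance or missing-data method. Section 11.2 asks only that missing data be explained in the CRF.

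**The concern.** The endpoint asks how PhA moves with response, so it needs patients from the whole range of response, measured at comparable times. As written, nothing secures a second measurement at a known time. A patient who feels well may see no reason to come back, and one who has given up on the therapy may go elsewhere. Either way, having a follow-up value becomes related to the explanatory variable.

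Losing patients from one or both ends of the response range narrows the spread of IBS-SSS change. That lowers the correlation, widens intervals and can shift the mean change. Because 11.4 names objective evaluation of treatment response as a purpose and says a larger study will be considered on the results, a weak or null finding here would be hard to read: it could reflect PhA, or who was measured.

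**Working it through.** **No plan figure to reproduce.** The documents give no alpha, power, effect size, SD or dropout rate. The only input taken from them is 20 IBS patients (11.4). Everything else below is an assumption chosen to show scale.

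**Assumptions.** IBS-SSS improvement and PhA change are bivariate normal, each in SD units, with true correlation 0.5. The test is two-sided at 5%. Loss is 30%, leaving 20 × 0.7 = 14 patients.

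**Formulae.** Let s be the SD of IBS-SSS change among those who return, relative to all patients.
- Correlation among returners: r = 0.5s / √(0.25s² + 0.75). This applies when loss depends only on IBS-SSS change.
- Power: Φ(√(n − 3) × atanh(r) − 1.96).
- Approximate standard error of the slope: √0.75 / (s√n) = 0.866 / (s√n).

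**Spread among returners.**
- Random loss: s = 1.
- Loss at random within the better-responding half: all of the lower 0.5 and 0.2 of the upper 0.5 remain. Mean = 0.798 × (0.2 − 0.5)/0.7 = −0.342; variance = 1 − 0.342² = 0.883; s = 0.94.
- Best 30% all lost (cut-off 0.524, normal density there 0.348): mean = −0.348/0.7 = −0.497; variance = 1 − 0.524 × 0.497 − 0.497² = 0.493; s = 0.70.
- 15% lost from each end (cut-offs ±1.036, density 0.233): mean = 0; variance = 1 − 2 × 1.036 × 0.233/0.7 = 0.310; s = 0.56.

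**Results.**

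| Scenario | n | r | √(n−3)·atanh(r) − 1.96 | Power | Slope SE | Shift in mean PhA change (SD) |
|---|---|---|---|---|---|---|
| No loss | 20 | 0.50 | 0.30 | 62% | 0.19 | 0 |
| 30% lost at random | 14 | 0.50 | −0.14 | 45% | 0.23 | 0 |
| 30% lost, within better half | 14 | 0.48 | −0.24 | 41% | 0.25 | −0.17 |
| Best 30% all lost | 14 | 0.38 | −0.65 | 26% | 0.33 | −0.25 |
| 15% lost from each end | 14 | 0.31 | −0.91 | 18% | 0.42 | 0 |

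The mean shift is 0.5 × the mean of IBS-SSS improvement among returners. A simulation of 2 million draws agrees for the correlation and power in the two one-sided scenarios.

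**Separating the two effects.** From 62% to 45% is the smaller sample alone. Selection adds 4 points in the mild case (45 to 41), 19 when all of the best 30% go (45 to 26) and 27 when both ends go (45 to 18).

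**Slope.** When loss depends only on IBS-SSS change and the relation is linear, the slope stays at 0.50, with lower precision as the table shows. When loss depends on both changes, it does not. In the simulation, dropping half or 90% of patients with a high sum of the two changes took the slope to 0.44 or 0.27.

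**The case against.** A reader might infer that follow-up happens only if the patient has a clinic appointment. The text does not say so: the same-day arrangement is a preference, which leaves room for a separate visit, and 8.2.3 plans visits in the plural for IBS patients. Nor does 8.2.4 forbid a last assessment; it only does not require one. What stands is that no such visit is scheduled.

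A reader might also infer that every early leaver is lost. Only a patient with no subsequent visit has no change value.

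A third tempting reading is that improvers are the ones who leave, so response is understated and the result biased towards null. The documents give no dropout rate and no reasons. Non-responders may leave as readily, which would push the mean the other way.

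The low power figures can mislead too. The 26% requires every top responder to vanish and nobody else. At 30% loss, most of the fall from 62% in the mild case is simply fewer patients. Section 7.3 does not prescribe a correlation, and a regression slope can survive selection on IBS-SSS change. This is a fair limit, but 11.4 names no analysis for the endpoint, so the slope cannot be assumed to be the estimate, and its precision suffers in any case.

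Lastly, the study is exploratory, the endpoint is secondary, and 11.4 sets no rule by which a null result would stop a larger study. All of that stands and limits the weight of the point.

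**Conclusion.** The concern holds in a limited form. In the text and activities table, nothing fixes when an IBS patient is measured again or ensures that it happens, and the stated preference ties it to clinic days. Whether and when a change value exists can therefore depend on response. The size and direction of any bias are unknown. The illustration, resting on an assumed correlation of 0.5 and 30% loss, runs from 45% power with no selection to 18% with loss at both ends, against 62% with complete follow-up. The correlation, precision and mean change are exposed; the linear slope is unbiased only if loss depends on IBS-SSS change alone.

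The documents do not support extending the point to the primary endpoint, which is set at visit 1: "The primary endpoint of this study is to explore whether PhA differs between IBS patients and healthy volunteers at visit 1". If the 6.6 schematic gives a follow-up time, the timing part of the point is met once 8.2.3 repeats it; the dependence on attendance remains. The change is worth making because a missed measurement cannot be recovered later, and enrolling more patients would restore precision without removing selection.

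**What to change.** **In 8.2.3 and 6.7 (the main change).** Set one follow-up assessment of BIA, IBS-SSS and IPAQ at a fixed interval after visit 1, with a window. It should apply to every IBS patient, whether or not a clinic appointment falls then and whether or not therapy was continued. Name it as the time point for the PhA-change endpoint in 7.3. The sponsor should choose the interval.

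**In 11.4.** Estimate the regression slope of PhA change on IBS-SSS change with its confidence interval. Report how many of the 20 have follow-up, and compare their visit-1 characteristics with those of patients who do not.

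**In 8.2.4 (secondary).** Offer the same assessment to patients who announce that they are leaving, and record the reason, keeping the pregnancy rule in 9.4. This cannot reach patients who silently stop attending, and a symptom score taken by telephone would supply no PhA, so it does not replace the fixed time point.

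**Cost.** Protocol wording, and at most one 30-minute visit outside a clinic appointment for up to 20 patients, using assessments already in the plan. Some patients may still not attend, which is why the follow-up count and the comparison are needed.

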8.2.5 End of Study

The study ends when the last study participant quits the study.

9 **Selection of Subjects**

9.1 Selection of Study Population

IBS patients will be recruited from the outpatient clinic at the Department of Gastroenterology and Hepatology of UZ Brussels. IBS is defined according to ROME IV criteria. Healthy subjects will be recruited by advertisement.

9.2 Inclusion Criteria

IBS patients:

- Patients aged 18 75 years;
- Fulfilling the ROME IV criteria for IBS;

For healthy volunteers:

- Patients aged 18 - 75 years;

9.3 Exclusion Criteria

- Clinical suspicion of an organic disorder different from IBS (patients can be included when this disorder had been excluded);
- Known inflammatory bowel disorder;
- Known major intestinal motility disorder;
- Alcohol (defined as more than 14 U per week) or other substance abuse;
- Active psychiatric disorder;
- Known systemic or auto-immune disorder with implication for the GI system;
- Prior abdominal surgery (with the exception of cholecystectomy or appendectomy);
- Any prior diagnosis of cancer other than basocellular carcinoma;
- Current chemotherapy;
- History of gastro-enteritis in the past 12 weeks;
- Dietary supplements unless taken at a stable dose for more than 12 weeks;
- Treatment with neuromodulators (one neuromodulator taken at a stable dose for more than 12 weeks is allowed);
- Pregnancy.

9.4 Contraception/Pregnancy Avoidance

As no intervention is planned, there is no specific requirement for contraception. However, no further data will be collected from pregnant subjects.

10 Study Assessments and Procedures

10.1 Study Assessments

10.1.1 Screening

At screening a subject's eligibility will be reviewed. Patients should fulfill the ROME IV criteria for IBS. This also includes a physical examination to rule out indications of a possible organic cause for the abdominal symptoms. If another cause of the symptoms is suspected based on history or clinical examination, it should be ruled out before inclusion.

Informed consent will be obtained during the screening visit prior to scheduling study assessments. Instructions about how to fill in the 4DFD will be provided.

10.1.2 First visit

Study participants should be fasting for 6h when attending the first visit.

The 4dFD should be filled in during the week preceding the visit. Clinical parameters of both IBS patients and healthy subjects will be recorded during the first visit.

During first visit, participants will fill in several questionnaires:

- IBS-SSS
- Psychological parameters:
 - o GAD-7
 - o PHQ-9
 - o PHQ-15
 - o VSI
- IPAQ

BIA will be performed.

